17. SAFETY OUTCOMES

All outputs for safety outcomes will be based on the Safety Analysis Set.

There will be no statistical comparisons between the treatment groups for safety data, unless otherwise specified with the relevant section.

17.1. ADVERSE EVENTS

An AE is defined as any untoward medical occurrence in a subject, temporally associated with the use of study treatment, whether or not considered related to the study treatment. An AE can therefore be any unfavorable and unintended sign (including an abnormal laboratory finding), symptom, or disease (new or exacerbated) temporally associated with the use of study treatment. All AEs will be coded to appropriate System Organ Class (SOC) and Preferred Term (PT) using Medical Dictionary for Regulatory Activities (MedDRA) central coding dictionary, Version 21.0.

Pre-treatment AEs are defined as AEs that begin before the initiation of the first dose of study drug administration on Day 1 but after obtaining informed consent and will be recorded as pre-treatment AEs. These events will be presented in the listings only and will not be included in the tabular summary of AEs.

Treatment-emergent adverse events (TEAEs) are defined as AEs that first occurred after the initiation of the first dose of study drug administration on Day 1 or a pre-treatment AE that worsened in severity. See APPENDIX 2 for handling of partial dates for AEs. In the rare case where it is not possible to assess treatment emergence, the AE will be classified as treatment emergent (i.e., the worst case).

Severity

AE severity will be classified as Mild, Moderate, or Severe as per protocol Appendix 4. TEAEs with missing severity will be classified as Severe. If subject reports a TEAE more than once within the same SOC/ PT, the AE with the worst-case severity will be used in the corresponding severity summaries.

Relationship to Study Medication

Relationship to study medication will be completed by the Investigator as per Protocol Appendix 4, classified as “Related” or “Not Related”. A TEAE is assessed as “Related” if there is reasonable/plausible possibility that the TEAE may have been caused by the study medication. A TEAE is assessed as “Not Related” if no causal relationship exists between the study medication and the TEAE, but an obvious alternative cause exists, e.g. the subject’s underlying medical condition or concomitant therapy. TEAEs with missing relationship to study medication will be regarded as “Related” to study medication. If a subject reports the same TEAE more than once within the same SOC/ PT, the AE with the worst-case relationship, i.e., “Related” to study medication, will be used in the corresponding relationship summaries.

All AE tabulations will be performed by treatment and with all active treated subjects combined overall as well as all placebo treated subjects combined from both cohorts displaying the number and percentage of subjects. Incidence of TEAEs will be tabulated as follows:

- Across System Organ Class (SOC) and Preferred Term (PT): serious TEAEs and those leading to death or study discontinuation, related TEAEs and serious related TEAEs, by severity, and related TEAEs by severity.
- By System Organ Class (SOC) and Preferred Term (PT).

- By System Organ Class (SOC), Preferred Term (PT) for TEAEs related to study medication.
- By System Organ Class (SOC), Preferred Term (PT) and maximum severity.
- By System Organ Class (SOC), Preferred Term (PT) and maximum severity for TEAEs related to study medication.

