7.1 Discontinuation of Study Treatment

Subjects should not receive further study treatment if one or more of the following criteria are met. It is not necessary to exit the participant from the study as long as they do not receive further study treatment. The Investigator may use their discretion in deciding whether to discontinue the participant from the study. If the subject is discontinued from the study early, see SoA (Section 1.3) for data to be collected at the time of study discontinuation. The reason that the study treatment is stopped should be documented on the appropriate eCRF.

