9.4.3 Safety Analyses

All safety analyses will be performed on the Safety Analysis Set.

Treatment-emergent adverse events (TEAEs) are defined as AEs that first occurred or worsened in severity after administration of study treatment.

Adverse events will be coded using the Medical Dictionary for Regulatory Activities (MedDRA). For each study treatment, numbers of TEAEs and incidence rates will be tabulated by preferred term and system organ class.

Treatment-emergent AEs by maximum severity, TEAEs by relationship to study treatment, SAEs, TEAEs leading to death, and TEAEs leading to discontinuation of study treatment will be tabulated for each study treatment.

All laboratory test results, vital signs measurements, and ECG results will be summarized for each treatment group using descriptive statistics at each visit for raw numbers and change from baseline.

Test results from otoscopy, tympanometry, nasal and epipharynx endoscopy, UPSIT olfactory test, and audiology pure tone hearing test will be listed and summarized as appropriate.

Additional details will be provided in SAP.

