4.3. CHANGES TO ANALYSIS FROM PROTOCOL

Pharmacokinetic analysis of CP will not be completed because the quantitative method for the determination of CP is not feasible. This resulted in the below changes from the protocol to the SAP:

Protocol	SAP
Secondary Objective : To evaluate if any systemic exposure of cholesteryl palmitate (CP) can be detected in serum at levels higher than endogenous CP levels in serum in up to 15 healthy adult volunteers who will be evaluated in the Cohort B dose (OP0210 60 mg per day) versus placebo.	To evaluate if any systemic exposure of cholesteryl palmitate (CP) can be detected in serum at levels higher than endogenous CP levels in serum in up to 15 healthy adult volunteers who will be evaluated in the Cohort B dose (OP0210 60 mg per day) versus placebo (if feasible).

Secondary Endpoint: Maximum baseline adjusted serum concentration (C_{max}) of CP on Day 14.	
Maximum baseline adjusted serum concentration (C_{max}) of CP on Day 14 (if feasible).
Secondary Endpoint : Time to maximum concentration (t_{max}) of CP on Day 14.	Time to maximum concentration (t_{max}) of CP on Day 14 (if feasible).

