8. STATISTICAL CONSIDERATIONS

8.1. SAMPLE SIZE DETERMINATION

The sample size is not based on statistical considerations, but is typical for studies of this nature, and is considered adequate to characterize the distribution of the planned endpoints.

There will be a total of 30 subjects; 2 dose cohorts of 15 subjects each. Subjects will be randomized in 4:1 (OP0201:placebo) ratio to receive either OP0201 or placebo within each dose cohort.

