10. DISPOSITION AND WITHDRAWALS

All entered subjects as defined in the Entered Analysis Set will be accounted for in this study. Subject disposition will be tabulated by cohort and treatment for number of subjects entered, randomized, treated, prematurely withdrew, completed study, and for each reason of premature withdrawal from the study along with the associated percentages. The percentages for the reason of withdrawal for screen failure subjects will be based on the entered set, whereas it will be based on safety set for treated subjects. The tabulation will also be presented for all active treated subjects, all placebo treated

Document: Statistical Analysis Plan
Author: [REDACTED]

Version Number: 2.0
Version Date: 03APR2019

[REDACTED]
[REDACTED]

subjects, and for all subjects combined from both cohorts, irrespective of treatment received, as Overall.

A listing will present dates of completion or early withdrawal and the reason for early discontinuation, if applicable, for each subject. Screen failure subjects will be listed indicating the primary reason of screen failure and will be included in disposition summary tabulations.

Listings of inclusion/exclusion criteria responses, study eligibility during screening and Day -1, and study treatment administration date and times will be provided.

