17.1.1. TEAEs LEADING TO DISCONTINUATION OF STUDY MEDICATION

TEAEs leading to permanent discontinuation of study medication will be identified by using the variable pertaining to Action Taken with Study Treatment on the Adverse Events page of the (e)CRF and will also be included in the Adverse Events listing.

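### SAP 17.1 names TEAEs leading to study discontinuation as its only tabulated discontinuation category, while the protocol prespecifies a table of TEAEs leading to discontinuation of study treatment

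*SAP*

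**What the plan says.** Protocol 9.4.3 sets out the safety summaries and includes this commitment: "TEAEs leading to discontinuation of study treatment will be tabulated for each study treatment". The synopsis carries the same commitment.

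Protocol 7.1 treats stopping treatment and leaving the study as separable: "It is not necessary to exit the participant from the study as long as they do not receive further study treatment". Exit from the study has its own section, 7.2.

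SAP 17.1 gives five bullets of AE tabulations. The first, an overview across system organ class and preferred term, covers "serious TEAEs and those leading to death or study discontinuation", together with related TEAEs and severity. The other four are breakdowns by system organ class and preferred term: all TEAEs, related TEAEs, and each of these by maximum severity. None mentions discontinuation of treatment.

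SAP 17.1.1 is headed for discontinuation of study medication. It gives a derivation, "TEAEs leading to permanent discontinuation of study medication will be identified by using the variable pertaining to Action Taken with Study Treatment", and says that these events "will also be included in the Adverse Events listing". It names no table.

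SAP 10 (disposition) tabulates subjects "for each reason of premature withdrawal from the study along with the associated percentages". SAP 4.3 declares one change from the protocol: "Pharmacokinetic analysis of CP will not be completed because the quantitative method for the determination of CP is not feasible".

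**The concern.** The protocol fixes the category to be tabulated and the SAP names a different one. The categories part company for one kind of subject: someone who stops the drug because of an adverse event and is then followed to Day 21. The protocol permits this, and it is a tolerability event.

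Safety and tolerability are the primary objective. The protocol states no hypotheses, and the SAP plans no statistical comparison of treatment groups for safety data unless otherwise specified. The descriptive tables therefore carry the conclusion. A discontinuation row built on the wrong category could read zero when a subject had come off treatment for an adverse event, and nothing in SAP 4.3 would alert the reader to the change of definition.

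**Working it through.** The documents state no figure on this point, so there is nothing to reproduce. The check is a comparison of texts, followed by a calculation of scale.

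**Where each type of subject would appear, on the literal wording**

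| Subject with a TEAE | Protocol 9.4.3 table | SAP 17.1 discontinuation row | SAP 10 study-withdrawal counts | SAP 17.1.1 listing |
|---|---|---|---|---|
| Stops drug and leaves the study because of it | yes | yes | yes | yes |
| Stops drug because of it, stays in the study | yes | no | no | yes |

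Only the second line differs. That subject's event is still counted in the system organ class and preferred term tables of SAP 17.1, by severity and relationship. The missed sprays still lower the compliance figures in SAP 15, against 168 expected sprays in Cohort A or 336 in Cohort B. The compliance summary does not attribute the missed sprays to an adverse event, however, and no summary named in the SAP text would show that a TEAE led to stopping treatment.

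**Scale**

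Inputs: two cohorts of 15, and "Subjects will be randomized in 4:1 (OP0201:placebo) ratio to receive either OP0201 or placebo within each dose cohort". This gives 15 × 4/5 = 12 active and 15 × 1/5 = 3 placebo per cohort. Pooled as in SAP 7.2, there are 24 active and 6 placebo subjects.

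Assumption, for illustration: exactly one subject in the column concerned stops drug for a TEAE and stays in the study, and no other subject discontinues. The percentage is x/n. Exact (Clopper-Pearson) 95% intervals are added only to show how little a single count says at these sizes; SAP 17.1 plans numbers and percentages for AEs, not intervals.

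| Column | Row on study discontinuation | Row on treatment discontinuation |
|---|---|---|
| One OP0201 dose group, n = 12 | 0/12 = 0% (0 to 26.5%) | 1/12 = 8.3% (0.2 to 38.5%) |
| All active, n = 24 | 0/24 = 0% (0 to 14.2%) | 1/24 = 4.2% (0.1 to 21.1%) |
| All placebo, n = 6 | 0/6 = 0% (0 to 45.9%) | 1/6 = 16.7% (0.4 to 64.1%) |

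The percentage is the weight of any one subject in the column. It is not a forecast.

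**The case against.** The best defence is that SAP 17.1.1 and 17.1.2 are definitions for categories already named in 17.1. The word *also* in 17.1.1 suggests that the listing comes on top of some other output. Section 17.1.2 likewise mentions only listings for SAEs, yet 17.1 plainly tabulates serious TEAEs, so silence about a table in 17.1.1 proves little. SAP section 17 gives no derivation for an AE leading to study withdrawal; the action-taken variable is the only discontinuation rule there. On this reading the row in 17.1 is already the protocol's row under a loose label. The protocol is loose too: its section 4.6.1 speaks of stopping treatment and of discontinuing the study in the same sentence. The silence of SAP 4.3 would then mean that no change was intended.

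This reading is possible and cannot be ruled out. SAP 9 says that the shells define the content of the tables, and the shells are not in the documents. It does not remove the point, though. If it is right, 17.1 and 17.1.1 use different terms for one row, and a programmer could build either version.

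A reader might go further and infer that subjects who stop drug but stay in the study are not counted at all, or are sent only to a listing. The documents do not support that. Section 17.1.1 identifies exactly these events, the general AE tables still count them, and *only* is not what 17.1.1 says. With 30 planned subjects and individual data listed, such a case would be visible in the reported data.

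**Conclusion.** The mismatch stands, in limited form. The SAP's only named discontinuation category differs from the one that the protocol prespecifies, the two can differ in practice under protocol 7.1, and SAP 4.3 declares no change. A listing of treatment discontinuations is assured; the tabulation promised in protocol 9.4.3 is not.

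Whether the finished table would actually omit anyone is not established. That depends on the unseen shells and on whether any subject stops treatment for a TEAE while remaining in the study; the documents give no expected number, and it may be zero. If there were one, a dose-group row could read 0/12 where the protocol's table would read 1/12. The information would be recoverable from the listings, so this is a modest fault. It is worth correcting because it affects a prespecified summary for the primary objective.

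**What to change.** In the first bullet of SAP 17.1, name TEAEs leading to permanent discontinuation of study treatment, derived from the action-taken variable as in 17.1.1 and tabulated by treatment. Keep TEAEs leading to withdrawal from the study as a separate row if wanted, with its own derivation. State in 17.1.1 that the events are tabulated as well as listed, and check that the table shell carries the same label. If the sponsor does intend to tabulate study discontinuation only, declare and justify that in SAP 4.3.

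The cost is one phrase and one table row. The variable is already collected, and no clinical rule or procedure changes.

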17.1.1. TEAEs LEADING TO DISCONTINUATION OF STUDY MEDICATION

TEAEs leading to permanent discontinuation of study medication will be identified by using the variable pertaining to Action Taken with Study Treatment on the Adverse Events page of the (e)CRF and will also be included in the Adverse Events listing.

17.1.2. SERIOUS ADVERSE EVENTS

Serious adverse events (SAEs) are those events recorded as "Serious" on the Adverse Events page of the (e)CRF. SAEs will be collected for all entered subjects and identified as such in the listings. An SAE is defined as any untoward medical occurrence that, at any dose results in 1 or more of the following outcomes: death, is life-threatening, requires in-patient hospitalization or prolongs existing hospitalization, persistent disability/ incapacity, is a congenital anomaly or birth defect, or other medically important event as detailed in the Appendix 4 of the study Protocol.

If any subject dies during the study as recorded on the adverse events page of the (e)CRF, the information will be presented in the SAE data listing.

17.2. OTOSCOPY

Individual results of all Otoscopy assessments will be listed including the result of overall assessment (Normal or Abnormal) as recorded on the (e)CRF. The frequencies of overall assessment results as well as the categorical response to each Otoscopy variable will be tabulated along with the corresponding percentages by ear (left and right) and treatment.

Each Otoscopy variable will be derived programmatically as Normal or Abnormal according to the following criteria description:

- Contour has the following categories: normal, retracted, full, bulging, perforated, or not assessable. Normal response will be interpreted as Normal whereas any other response will be interpreted as Abnormal.
- Color has the following categories: normal, partly red, completely red, or not assessable. Normal response will be interpreted as Normal whereas any other response will be interpreted as Abnormal.

Document: Statistical Analysis Plan
Author: [REDACTED]

Version Number: 2.0
Version Date: 03APR2019

[REDACTED]

- Fluid has the following categories: No or Yes. The interpretation of normal/abnormal will be as follows: response of No will be interpreted as Normal; whereas a response of Yes will be interpreted as Abnormal. If the response is Yes indicating the presence of fluid behind the tympanic membrane, then the color of fluid is also recorded (yellow, translucent, red, blue, black, or clear).
- Translucency has the following categories: translucent, semi-opaque, opaque, or not assessable. The response of translucent will be interpreted as Normal whereas other responses will be interpreted as Abnormal.

Shifts from baseline to each post-baseline visit will be tabulated by ear and treatment for the results of assessments derived above as Normal or Abnormal. The shift tables will present the frequency and the corresponding incidences along with the 95% CI for the incidences.

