8.2.5 Otoscopy

Otoscopy will be performed to assess the appearance of the tympanic membrane (normal or abnormal). If abnormal, then it will be rated for the following variables:

- Contour (retracted, full, bulging, perforated).
- Color (partly red or completely red).
- Color of fluid behind the tympanic membrane (yellow, dark red, bright red, green, or clear).
- Translucency (semi-opaque, opaque).

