7.2. TREATMENT SUMMARIZATION

In general, unless otherwise stated for specific endpoints in the respective sections of this document, data will be presented for each treatment group, with placebo subjects from both cohorts combined into a single, overall placebo group. Data for all active treated subjects and for all treated subjects combined will also be presented when appropriate.

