7.5. BASELINE

Baseline is defined as the last scheduled non-missing measurement taken prior to dosing and will

Document: Statistical Analysis Plan
Author: [REDACTED]

Version Number:
Version Date:

2.0
03APR2019

correspond to: Screening assessment for clinical laboratory; Day -1 assessment for Vital Signs; Day 1 pre-dose assessment for ECG in Cohort A, and the average of the mean triplicate ECG assessments at Day 1, 60 minutes pre-dose and Day 1, 30 minutes pre-dose for ECG in Cohort B; Screening assessment for Physical Examination; Day -1 assessment for Otoscopy, Tympanometry, and Nasal and Epipharynx Endoscopy ; and Screening assessment for University of Pennsylvania Smell Inventory Test (UPSIT) Olfactory test, and Audiology Pure Tone hearing test. However, if a subject is missing the planned baseline collection then the last non-missing evaluation prior to dosing (scheduled or unscheduled), if available, will become the baseline value.

For PK assessments, baseline serum concentration is defined as the mean of the two predose serum concentrations observed in samples collected on Day 1 prior to the first dose. If one predose sample is missing, the other Day 1 predose concentration will be used for baseline correction.

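### SAP 17.2 derives a *not assessable* otoscopy rating as Abnormal, so the shift tables count unreadable ears as new abnormalities and can hide real ones

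*SAP*

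**What the plan says.** SAP 17.2 derives each otoscopy component as Normal or Abnormal by program. The contour levels are normal, "retracted, full, bulging, perforated, or not assessable. Normal response will be interpreted as Normal whereas any other response will be interpreted as Abnormal". The color levels are normal, "partly red, completely red, or not assessable. Normal response will be interpreted as Normal whereas any other response will be interpreted as Abnormal". Translucency also has a *not assessable* level, and there "The response of translucent will be interpreted as Normal whereas other responses will be interpreted as Abnormal". Fluid is recorded only as No or Yes.

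Shifts from baseline to each later visit are then tabulated from these derived values, by ear and treatment: "The shift tables will present the frequency and the corresponding incidences along with the 95% CI for the incidences". The SAP gives no separate shift category, exclusion or denominator rule for *not assessable*.

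SAP 7.5 sets the otoscopy baseline at Day -1 ("Day -1 assessment for Otoscopy, Tympanometry, and Nasal and Epipharynx Endoscopy"). If the planned baseline collection is missing, "the last non-missing evaluation prior to dosing (scheduled or unscheduled), if available, will become the baseline value". SAP 7.2 presents each dose group, "with placebo subjects from both cohorts combined into a single, overall placebo group".

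**The concern.** *Not assessable* means that no rating was obtained. It is not evidence of an abnormal membrane. Forcing it into the Abnormal level distorts the shift table in both directions. After dosing, it creates abnormalities nobody saw. At baseline, it removes the ear from the group in which a new abnormality could be counted. The second direction works against detecting harm, so the rule cannot be defended as a worst-case convention.

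Otoscopy is named among the primary safety endpoints (SAP 3.1), and the product acts on the Eustachian tube, so readers will look at these tables. With 12 subjects per dose and 6 on placebo, a single ear changes the reported incidence visibly. The error can inflate OP0201, inflate placebo (which flatters OP0201), or hide a new finding.

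**Working it through.** The documents state no otoscopy rate or shift count, so there is no planned figure to reproduce. The check traces each recorded response through the rule and then sizes the effect.

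**Tracing the rule (contour, color, translucency)**

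| Day -1 | Post-dose visit | Tabulated as | Effect |
|---|---|---|---|
| Normal | Not assessable | Normal to Abnormal | False new abnormality |
| Not assessable | Truly abnormal | Abnormal to Abnormal | New abnormality not shown as new |
| Not assessable | Normal | Abnormal to Normal | False improvement |

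The baseline fallback does not rescue the last two rows. It applies when the planned collection is missing, and a recorded *not assessable* is a collected response. The Screening otoscopy in the Schedule of Activities is therefore not used.

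**Inputs**
- OP0201 group size: 12 per dose (SAP Table 1).
- Pooled placebo: 3 + 3 = 6 (SAP Table 1, SAP 7.2).
- Tables are by ear, so each subject contributes one ear to a cell.
- Interval: exact Clopper-Pearson at 95%, an assumption because the SAP names no method. For x events in n, the lower limit is the 0.025 quantile of Beta(x, n − x + 1) and the upper limit is the 0.975 quantile of Beta(x + 1, n − x). For x = 0 the lower limit is 0 and the upper limit is 1 − 0.025^(1/n).

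**Case 1: one ear Normal on Day -1 and unreadable after dosing, with no true abnormality in the group**

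| Group | As written | Unreadable ear set to missing |
|---|---|---|
| OP0201 dose group | 1/12 = 8.3% (0.2 to 38.5) | 0/11 = 0% (0 to 28.5) |
| Pooled placebo | 1/6 = 16.7% (0.4 to 64.1) | 0/5 = 0% (0 to 52.2) |

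**Case 2: one OP0201 ear Normal at Screening, unreadable on Day -1, truly abnormal on Day 14**

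| Handling | Normal-to-Abnormal incidence |
|---|---|
| As written, all ears in the denominator | 0/12 (0 to 26.5) |
| As written, only baseline-Normal ears in the denominator | 0/11 (0 to 28.5) |
| With Screening as the fallback baseline | 1/12 = 8.3% (0.2 to 38.5) |

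Both denominators are shown because the SAP defines none for the shift incidence. Setting the Day -1 value to missing without the fallback would still leave this ear out, at 0/11, so the fallback is a necessary part of the correction.

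**How often a false shift would appear.** The rate q of unreadable ears is not in the documents. The chance of at least one false Normal-to-Abnormal shift in one cell (one ear side, one component, one visit, all ears Normal at baseline) is 1 − (1 − q)^n:

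| Assumed q per ear-visit | n = 12 | n = 6 |
|---|---|---|
| 1% | 11% | 6% |
| 2% | 21% | 11% |
| 5% | 46% | 27% |
| 10% | 72% | 47% |

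**The case against.** - **The eCRF may prevent the main case.** Protocol 8.2.5 says of the membrane: "If abnormal, then it will be rated for the following variables", and lists no *not assessable* level. If components are collected only for ears already called abnormal, Case 1 largely disappears. The eCRF is not shown. The SAP levels normal and translucent hint that components are collected for all ears, but they fit either design. This limits how often the problem arises. It does not make the component derivation right, because an unrated component would still be called Abnormal.
- **It is a conservative convention.** After dosing, the rule resembles the SAP's worst-case handling of missing AE severity and relationship (SAP 17.1). At baseline it is the opposite of conservative, and SAP 17.2 offers no worst-case rationale.
- **Retests could cure it.** SAP 7.6 substitutes a retest when a scheduled result is flagged invalid, and subjects are resident, so a repeat look is practical. But nothing flags *not assessable* as invalid, and letting unscheduled results feed a worst-case value would not displace a derived Abnormal.
- **Unreadability may be informative.** Dropping such ears could lose a signal. That is a reason to keep the count visible in the frequency table, where it already appears, not to label it Abnormal.
- **The impact is small.** This stands in part. The tables are descriptive, SAP 17 plans no safety comparison between groups unless a section says otherwise, and the stopping rules in protocol 4.6.3 do not use them. The intervals overlap heavily, and in the All Active column one ear is only 1/24 = 4.2%. Listings, raw category frequencies and the recorded overall result keep a true abnormality in view. However, the overall result has no stated shift table, so the affected components supply all the planned otoscopy shifts except fluid.

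**Conclusion.** The concern holds: the rule is wrong as written for contour, color and translucency. Followed literally, it misreports the shift incidence and its interval for a primary safety endpoint, by 8.3 percentage points per ear in a dose group and 16.7 in pooled placebo when all subjects are in the denominator. The error can go in either direction. It is confined to the derived component values and their shift tables. Fluid, the recorded overall assessment, the listings and the raw frequencies are unaffected.

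The reading of the rule is certain. Its practical effect depends on how often *not assessable* is recorded, which is unknown and could be zero in healthy volunteers. The intervals rest on the exact method and the denominators stated above. The correction should be made, but it does not threaten the trial's overall conclusions.

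**What to change.** In SAP 17.2:

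1. Treat *not assessable* as missing in the Normal/Abnormal derivation and in the shift tables, and keep it as its own level in the frequency table as already planned.
2. State that the SAP 7.5 fallback to the last earlier pre-dose evaluation applies when a Day -1 component is *not assessable*.

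It would help to name the denominator of the shift incidence and the CI method in the same edit, since both are currently open. Only if the eCRF turns out to collect components solely for abnormal ears, add that an uncollected component in an ear recorded as Normal overall is derived as Normal. A recorded value, including *not assessable*, should never be overwritten.

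The cost is two sentences and a small programming change, with no new data. It should be settled before unblinding so that results cannot influence the choice. The only loss is that n in some shift cells falls by the few unreadable ears.
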